5.1 Informed Consent Procedures

Upon showing interest in the study, participants will be given a Participant Information Sheet (PIS) (appendix 1) by email or post, to explain in detail what the study involves, their role within the trial, highlight the anticipated benefits and hazards of the study. This is then further accompanied by an introductory call, for eligible participants, to discuss the PIS and run through the consent form (template is in appendix 2). After this call, the consent form will be emailed to the participants to digitally sign online (Qualtrics form).

Adequate time between reading the PIS and consenting will be given, to ensure there is time allocated for follow up questions on behalf of the participant.

The PIS will be updated and recirculated in the event of any new information or protocol deviations, to confirm participants wish to continue taking part.

Clear indication of withdrawal rights will be made known at each point of contact.

The lead investigator and trial coordinator, [name], has received inhouse training on Good clinical practice, as well has covered informed consent practises through the Human Tissues Act training. She will be registered on the site delegation log.

Due to the remote nature of the initiation of the trial, informed consent will be provided remotely, to reduce participant burden.

5.2 Risks/burdens

Venepuncture

Foreseeable discomfort may be experienced with the venepuncture such as:

- Stress regarding the process
- Insertion of the needle
- Minor bleeding on the area where the needle was inserted. This will be covered with a bandage to minimise the bleeding and reduce skin exposure.
- Minor bruising and/or irritation on the skin. This is normal and will typically last 2-3 days.

- A sore arm. This is normal and will typically last 1-2 days.
- During and/or after the blood sample, a participant may feel dizzy and/or faint. Should fainting occur, the participant will receive all the medical care required until they are fit to leave the Metabolic Research Unit.

To minimise these risks, a trained phlebotomist will conduct the venepuncture procedure.

Equipment

For some volunteers, the requirement of self-applying equipment might cause some stress regarding technical capabilities. To reduce this all volunteers will be well trained through supplied multimedia resources, a 1:1 induction with a study team member and will have continued access to the study team in case of any queries.

CGMs may cause slight discomfort in their application, as a very small needle will puncture the skin to sit just below the skin which will measure interstitial fluid glucose levels. As the sensor protrudes a few cm above the skin, there is a small risk that the sensors can get caught on everyday objects and rip out. To reduce this risk, sensor patches will be provided to cover the whole sensor and keep it fixed to the arm. There may be minor bleeding from the insertion of this needle, in which case participants are instructed to apply some pressure. If the bleeding does not stop after a few minutes of applying pressure, the sensor will be removed and reported to the study team. There is also the possibility of skin irritation to adhesives. If this is the case, the CGM should be removed, and the research team should be instructed for further action.

Participant burden

The initial screening and run-in session (as outlined in section 3.4, study flow), will be held remotely, via online documents and video/telephone calls. This we believe will reduce participant burden in needing to attend in-person clinics, thereby increasing study retention, and may further increase the comfort of the individuals.

The volunteer will attend 4 events: An introductory call, a virtual run-in, and a baseline and endline clinic. Additionally, they will be required to apply and wear study equipment and take urinary samples. To negate this burden, participants will be paid upon completion of the study for their time. Even if participants do not complete the study, pro rata payments will be made.

Dietary intervention

Potatoes contain a natural group of toxins called glycoalkaloids, which are harmful to health in vast consumption, and can cause gastrointestinal symptoms, such as nausea, vomiting and diarrhoea (68). Guidelines at the grower level restrict the amount of these toxins available for consumption, to a maximum value of 200mg/kg of fresh weight potatoes (69). Despite this, these toxins can become concentrated within the sprouting nodules (lenticels), of aging potatoes. To reduce risks of glycoalkaloid consumption, participants will be instructed on how to store their potatoes to increase

their shelf life, as well as reducing light exposure, and will be provided with a picture of a germinating potato of what not to consume. Additionally, cooking and preparation methods can significantly reduce the glycoalkaloid concentrations (70), which will be utilised in the recipe instructions.

With a change in diet, especially one with increasing fibre, it is possible volunteers may experience some changes in gastrointestinal motility and discomfort, such as bloating, diarrhoea or constipation. Any adverse effects should be immediately reported to the study team who will assist and provide guidance as to how to best continue.

Incidental findings

The detection of adverse or incidental findings such as undiagnosed dyslipidaemia, pre-diabetes or diabetes may arise following the fasted blood samples obtained during the baseline and endline visits. Should the blood samples result in out-of-range values, the volunteer will be informed by phone (or by email) and will be referred to their general practitioner (GP).

Weekly blood pressure outputs from each participant will be monitored throughout the study. If blood pressure readings result out of range, the volunteer will be supplied with a letter to take to their GP for further investigation.

Additionally, the use of the doppler ultrasound may highlight abnormalities in arterial health. Should this be the case, the same processes above are to be followed.

Any out-of-range results will only be shared with the participant. The participant will be supplied with a letter addressed to their GP and with a copy of their results. This will be recorded in the case report form and the volunteer will be excluded from participating in the study.

5.3 Screening Procedures

Online screening via Microsoft form. Location at the discretion of the volunteer. 30-60 minutes.

Participants will complete an online questionnaire screening session where they will be screened against the eligibility criteria (template for this is in appendix 3). The food survey will be specifically designed to ascertain if participants habitually consume <4 fruits and vegetables/day, habitually consume wholegrains, and if they do not consume red meat.

We estimate this not to exceed 30-40 minutes.

Data will then be reviewed by the study team, who will contact eligible participants to progress. Those who do meet the criteria will also be informed and thanked for their interest.

5.4 Randomisation Procedures

Participants will be randomised to either the intervention or control arm, with an allocation ratio of 1:1. A minimisation procedure will be used that considers gender, age, ethnicity, BMI) in the randomization, by using the Shiny App software, which can be accessed at:

https://fsella.shinyapps.io/VM_app/?_ga=2.186170153.125318758.1628174827-961835063.1626383516 (71).

Screening data will be entered into minimisation software, by the research lead (See randomisation SOP). This database will balance the treatment arms for the following variables:

1. *Gender*. 2 groups: Male; Female
2. *Age*. 2 groups: 40-59; 60-80 y
3. *BMI*. 2 groups: Healthy weight 18.5-24.9; Overweight-Obese ≥ 25

Randomisation codes will be generated by the software and recorded on the relevant documentation in the Case Report Form and enrolment log. The randomization protocol follows the same protocol as used previously by our group for a parallel, two-arm, randomized controlled trial (30) for which a study statistician was employed. It has not been deemed necessary to employ a study statistician on the current trial due to the similarity of the study design, but the protocol will be discussed with a statistician from the King's Joint Clinical Trials Unit.

Participants will be blinded to whether they are receiving the intervention or the control, but it is not possible to blind them to the food itself. Also, as the study team is limited by resources, observer blinding is also impossible; however, the researcher undertaking statistical analysis will be blinded prior to analysis using a second set of study ID codes. FMD analysis will be conducted through semi-automated software analyses, which will reduce bias.

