3.3 Outcome variables

Primary Outcomes

Sleep efficiency: As aforementioned, increased dietary potassium may plausibly modify sleep quality, as previously seen in an interventional study by Drennan et al (46), through mediation of improvements to autonomic function (19) and improved vascular function by restoring baroreflex function (15) and improving endothelium-dependent vasodilation (47).

This is measured by using 7-d wrist actigraphy (MotionWatch8, CamNTech Ltd, Cambridge, UK) according to previously published procedures (7). Sleep quality (%) is measured as the amount of time spent asleep/ total amount of time spent in bed.

12-day mean nocturnal glucose: Potatoes may improve nocturnal glucose through several pathways, involving increased dietary quality (48), such as increased vitamin C (49), increased dietary potassium (50) and increased satiety, when compared to alternative starches (51).

Nocturnal measures were chosen to assess glycaemic regulation without the confounding influence of food intake. Whole sleep-time glycaemia parameters will be analysed is, and further sub analysis will

be done pre- and post-sleep, and mid-point to investigate potential differences according to sleep stages.

CGM (Abbott Freestyle Libre 3) will be used to measure glycaemic control for 12 consecutive days. The principal investigators have recently reported on the high precision of the Abbott CGM (52). Twelve days has been selected as the 1st and last day of the CGM period may give unreliable results, therefore day 1 and 14 will be excluded from the analysis.

Secondary outcomes

Other nocturnal glucose markers: We will further analyse 12-day nocturnal area under the curve, glycaemic variability (GV), time in range non-diabetic population (TIR_{ND}). GV reflecting glucose fluctuations, are more strongly associated with oxidative stress than prolonged elevated glucose and glucose nadir and peaks, including the number and size (% change from pre-meal baseline) due to the association of glucose nadirs with hunger, satiety, alertness and energy intake (at subsequent meals and over 24 h period) (53) and peaks with oxidative stress and impairment in glycaemic control. Increased TIR_{ND} is associated with improved cardiometabolic markers (lower HbA1c, HOMA-IR, and 10-y ASCVD risk) and with poorer glucose tolerance when TIR is low (higher 1- and 2-h OGTT glucose) (54).

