Doppler ultrasound videos will be analysed using automated software (unnamed thus far) with our collaborators in Maastricht university, Netherlands. No laboratories will be required for their analysis.

Ideal parameters for %FMD are between 5-8%, but this can vary on the population. As there is considerable overlap between healthy and non-healthy populations (72), there are no out of range values considered in the analysis.

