Full samples will be brought into clinic at baseline and endline and will be processed by the study lead, or delegated research student.

For the midline measure, to reduce participant visits, they will be asked to record the full weight of the 24-hour urine sample using scales that are provided by the study team. They will then be responsible for mixing the sample and carefully decanting their sample with use of a funnel, into a 20mL subsample tube. These samples will be sent to KCL via usual courier services (royal mail or UPS) for the same day delivery. These will be packaged in line with dangerous substances regulations, as a category B parcel, and will be packaged to comply with packaging instruction 650. Once these parcels have been received by the study team, they will be processed in the laboratory by the study team.

Participants must fill out urinary collection forms (appendix 5), to accompany the samples at each time point.

Sample Labelling:

All participants will be assigned a unique study ID code. Participant documentation and specimens will be labelled with the unique study ID code which is a pseudonymised code used on all study documents and samples. There will be no identifiable information recorded on participant documents or samples. The study ID code will take the following format:

STY/PARTICIPANT_ID/
STUDY_TIME_POINT/PARTIICPANT_ID/ANALYTE

STY – STARCHy trial

STUDY TIME POINT – Baseline or Endline

ANALYTE – e.g., GLUC (glucose), INS (insulin)

Sample Logging and sample chain

Fasting bloods

The fasting blood samples collected at baseline and at the end point will be sent altogether to Affinity Laboratories in one batch on dry ice following storage at -80°C in a secure freezer in the Department

of Nutritional Sciences laboratory, following processing specifications. A sample accountability log and a box map of the samples will be inserted into the cryogenic storage boxes and emailed to the recipient ([name]).

All samples will have the appropriate accompanying documents and will be appropriately packaged and sent to [name] at Affinity Biomarker Laboratories.

Urine

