9.2 Case Report Form

Digital Case report forms (CRFs) will be completed by the PhD student, or trained delegate student. They will be completed after every study visit. The following will be included in CRFs:

1. Inclusion/exclusion criteria
2. Randomisation form
3. Date of informed consent
4. Date of birth
5. Current medications
6. Notes of participant's general wellbeing on study days
7. Participant eligibility prior to study days: i.e., adherence to diet intervention and fasting protocol
8. Visit dates
9. Visit number
10. Participant randomisation number
11. Blood glucose (from finger prick test)
12. Blood pressure measurements
13. Weight
14. Waist circumference
15. Body composition (%body fat).
16. Notes and checklists for:
 - 24-hour urine
 - HRV
 - FMD
 - Aktiia BP watch
17. Urine collection form
18. Copy of data from home data diaries:
 - Home weight measures
 - Evening meal adherence checklist
 - Sleep and wake times
19. STROOP test time, and results.
20. Any study interventional delays and reasons if able to state
21. AEs
22. Page for toxicities
23. Withdrawal from study
24. Study completion
25. Follow up of outcomes
26. Death
27. SAE form
28. Comments form

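### The plan masks the analyst but not the earlier scoring of recorded files; its second set of ID codes could cover that step at little cost

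*Combined protocol and SAP*

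**What the plan says.** Section 5.4 (Randomisation Procedures) sets out the blinding. The reason for leaving observers unblinded is given as "as the study team is limited by resources", and the statement is that "observer blinding is also impossible; however, the researcher undertaking statistical analysis will be blinded prior to analysis", by means of a second set of ID codes. The masked person is a researcher, since "It has not been deemed necessary to employ a study statistician on the current trial". The one safeguard stated for scoring is that FMD analysis is semi-automated, which the plan says will reduce bias.

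The outcomes at issue are these:
- **Sleep efficiency (primary).** Section 3.3 takes it from 7-day actigraphy, following a cited published procedure: "Sleep quality (%) is measured as the amount of time spent asleep/ total amount of time spent in bed". The study pack includes a diary that covers sleep, and the case report form receives a copy of the participant's "Sleep and wake times" (Section 9.2).
- **Nocturnal mean glucose (primary).** The synopsis defines it over sleep, from CGM. Section 3.3 fixes in advance that days 1 and 14 are dropped.
- **FMD (secondary).** Section 3.3 names a custom MATLAB program. Section 5.9 says "Doppler ultrasound videos will be analysed using automated software (unnamed thus far) with our collaborators in Maastricht university, Netherlands".
- **Heart rate variability (secondary).** Section 3.3 says that named software calculates the parameters from ECG recordings.

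The case report form in Section 9.2 also holds the randomisation form and the evening-meal checklist, and is completed by the PhD student or a delegate. The research lead enters the data for minimisation (Section 5.4). The pseudonymised study ID in Section 6.1 carries a visit label ("STUDY TIME POINT – Baseline or Endline") but no arm.

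**The concern.** Masking the final regression does not remove judgement already built into the values that enter it. If a person who knows the arm chooses an in-bed window, a sleep window for glucose, an FMD frame or an ECG segment, the choice is fixed before the masked analyst sees the data.

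The claim of impossibility is broader than its reason supports. Live contacts, dietary consultations, FMD acquisition and clinic measurements cannot readily be masked by a small team. Stored files are different: they are processed after collection, and the plan already intends to create the codes that would mask them. Participants know what they eat and the team delivers the diet, so file scoring is one of the few stages left where masking is practical. Both primary outcomes pass through it.

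**Working it through.** **1. The plan's own figure.** Section 4.1 gives a glucose difference of 0.468 mmol/L, SD 0.61, significance level 0.025 and 34 per arm. The noncentrality is 0.468 / (0.61 × √(2/34)) = 3.16 on 66 degrees of freedom. Two-sided at 0.025, this gives 80.5% power, against 79.2% at 33 per arm, so 34 reproduces. Allowing for dropout, 68 / 0.85 = 80. The sleep-efficiency calculation (4.2 points, 24 people) cannot be reproduced, because its SD is not given. Masked scoring changes none of these figures.

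**2. What is masked at each stage.**
- Live contacts and clinic measurements: unblinded (Section 5.4).
- Scoring of actigraphy, CGM and ECG files: nothing stated.
- Scoring of FMD videos: semi-automated and done with outside collaborators; whether the readers know the arm is not stated.
- Statistical analysis: masked by the second codes (Section 5.4).

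**3. Sensitivity of sleep efficiency to the in-bed window.** The minutes are assumed, chosen to fit the entry rule of below 85%. The shift is 100 × TST / (TIB − s) − 100 × TST / TIB, where TST is time asleep, TIB is time in bed and s is the number of minutes trimmed, all taken to be wake. For 400/480, the starting value is 83.33%:
- s = 5: 400/475 = 84.21%, a shift of 0.88 points; 0.88 / 4.2 = 21%.
- s = 10: 400/470 = 85.11%, a shift of 1.77 points; 1.77 / 4.2 = 42%.
- s = 15: 400/465 = 86.02%, a shift of 2.69 points; 2.69 / 4.2 = 64%.

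For 380/480 and 360/450 the shares are 20–21%, 40–43% and 61–66%. These are shifts in one recording. They become a between-arm bias of that size only if they are the net average difference between arms.

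**4. What a between-arm bias would do, if there were one.** The biases here are assumed. With no true effect, 34 per arm and an unadjusted two-sample t-test at two-sided 0.025, the noncentrality is b / (SD × √(2/34)), where b is the bias.
- Sleep efficiency, SD 4.59 (implied if the 24 people are per arm): b of 0.5, 1 or 2 points gives a false-positive rate of 4.0%, 8.8% or 31.6%.
- Sleep efficiency, SD 3.14 (implied if the 24 are the total): 5.7%, 17.0% or 63.0%.
- Glucose, SD 0.61: b of 0.05, 0.1 or 0.2 mmol/L gives 3.3%, 5.9% or 18.0%.

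The documents give no basis for choosing among these biases.

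**The case against.** A reader might infer that the scorers are unblinded. The documents do not establish this. The word observer may refer only to the live contacts, which indeed cannot be masked. FMD videos are read with collaborators at another university who have no described contact with participants, and the study ID shows no arm, so FMD reading may already be masked in practice. Hand editing of ECG files and manual setting of sleep windows are not described. The cited actigraphy procedure may fix the in-bed rule, and the CGM day exclusions are set in advance. All of this stands, and it limits the point to what the plan permits.

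A reader might also take the visit label as a source of bias. It is a weak one: a scorer who knows the visit but not the arm cannot favour an arm.

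The diary points partly the other way. If participants' own sleep and wake times set time in bed, the participant fixes the denominator, and relabelling files does not change that. This stands too.

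Finally, masking is not free. It needs a key holder who does not score, and scorers who work without the case report form. This cost is real but small, because masking the analyst already requires someone to hold a key, although the plan names no one.

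These objections do not supply the missing safeguard. Semi-automated software reduces a reader's input without masking the reader. The sleep and wake times sit in the same form as the randomisation record and the meal checklist.

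**Conclusion.** The point holds as a gap in the masking plan. Section 5.4 treats observer blinding as impossible across the board, masks only the analyst, and leaves the scoring of both primary outcomes and two secondary outcomes open to someone who knows the arm. Unblinded scoring is permitted, not proven.

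The 0.9 to 2.7 point shifts are a conditional ceiling. They assume that a person sets or edits the window, that the trimmed minutes are wake and, for bias, that the shift differs by arm. Errors unrelated to arm add noise only. The gain from masking is probably largest where a reader makes choices (FMD, actigraphy windows, any ECG editing) and smallest for the CGM mean; that ranking is a judgement and is not in the documents. This is a cheap improvement that should be made, and it does not show that the results are biased.

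**What to change.** In Section 5.4 (Randomisation Procedures), replace the general statement with the following:
- Live contacts, FMD acquisition and clinic measurements are unblinded.
- FMD, actigraphy, CGM and ECG files, with any diary sleep and wake times needed for scoring, are relabelled with the second ID codes. They are scored masked to arm, and to visit where feasible, without use of the case report form or meal checklist.
- A named person who does not score, the same one who holds the key for the analyst masking, keeps it until scoring and exclusions are locked.
- Files go to the FMD collaborators under masked codes only.

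Sections 3.3, 5.4 and 5.9 should also agree on the FMD software and on who reads the videos.

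Version 5.1 is dated 31 August 2025, after the estimated primary completion of 01/05/2025, so some files may already have been scored. If so, apply the rule to the remaining files and report which were scored masked.

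The cost is the recoding work, a key holder kept out of scoring, and a short delay before scoring starts. No visits, participants or additional readers are needed.

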5.4 Schedule of Treatment for each visit

Details of screening methods are summarized in Section 5.3

NB: All times allocated are estimates. Although the study team endeavours to keep within the limits of these suggestions, there may be deviations due to unprecedented circumstances or varying participant needs.

1st contact: Email exchange, online.

Upon responding to advertisements, volunteers will be emailed a participant information sheet, and an electronic questionnaire (via Qualtrics software). All forms will be reviewed by a study team member and will be assessed against inclusion/exclusion criteria. Participants will be informed the outcome at the earliest opportunity. If eligible, participants will then be invited to attend an introductory call.

2nd contact: Introductory call. Location, online, to be held at the discretion of the volunteer. 15-30 minutes.

All eligible participants will receive a telephone/video call (depending on the participant's preference) with a member of the study team, both to introduce themselves and the study. The information sheet will be discussed, and the consent form will be introduced. This call will serve as a chance for participants to ask questions and have their understanding of the study checked before giving

consent. This call also allows the study team to build rapport with participants. After this call, a consent form (online form), will be emailed out, and upon return, they will be invited to a virtual 1:1 run-in induction.

Once consent is obtained, participants will be posted a '**study pack**' consisting of:

1. Participant information guide
2. Study diary for writing data (sleep, BP, weight, evening meal compliance checklist)
3. Recipes
4. Equipment
 - a. CGM (primary outcome)
 - b. Motion Watch (primary outcome)
 - c. Aktiia blood pressure bracelet (secondary outcome)
 - d. 24-hour urine collection kits (X3) (adherence)
 - e. Kitchen Scales (to weigh 24hr urine at midline)
 - f. Bathroom scales (only if participant does not own any, secondary outcome)
5. Equipment leaflets, including SOPs with photos for guidance.
6. 4-day food diary incl VAS for appetite (X3)
7. Packaging to post equipment/diaries

3rd contact: Virtual (or in-person) run-in. Location at the discretion of the volunteer. 60 minutes.

Before this session, volunteers will be given leaflets and videos on the equipment they will apply and/or measure to give them a good understanding.

This follow-up session will be an overview and a chance for participants to ask outstanding questions. This will ensure that the study lead is happy that participants have suitable understanding of the process and are happy to continue with the process.

A summary of the training needs that will be addressed are written below:

Self-taken measurements include:

1. Body weight with home scales (Weekly, from wks.0 - 12)

Need to apply the following equipment alone:

1. Motion watch (7days)
2. Aktiia bracelet (7 days)
3. CGM (12 days)

Participants will be made aware that they are able to contact the study team at any time when they need. The contact details (study email and phone number) will be provided in the participant information guides they receive along with their equipment, as well as on email invitations.

4th contact: Clinic visit 1 (Wk 0), MRU at KCL. ~130 minutes.

The study team will have correspondence with participants to arrange a suitable date for their baseline clinic visit.

Participants will attend the MRU, 4th Floor, Franklin Wilkins Building, Kings College London and have the following procedures:

1. Urine samples collected (~0 mins)
2. Finger prick blood test (~10 minutes)
3. Blood pressure (~10 mins)
4. Fasted bloods (~20 mins)
5. Heart rate variability monitor fitted (ECG), to keep on for 48-hours (~10 mins)
6. Ultrasound imaging (~30 mins)
7. STROOP test (~15 mins)
8. Body composition and waist circumference (~10 mins)*
9. Questionnaires (ZOE FFQ) (~15 mins)
10. Dietary consultation (20 mins)***

*Optional break for a snack post measurements.

**Participants will then be instructed to start the dietary protocol after 48 hours after the baseline clinic, when participants' baseline HRV has been recorded.

***Participants will be required to attend a brief consultation with the associate nutritionist on the dietary intervention they have been assigned to. This will cover cooking methods, appropriate food items, and menu card run throughs. It will also provide an opportunity to problem-solve around identified conflicting commitments such as holidays or celebrations, where the participants may not be able to follow the intervention. Standardised advice on eating out will be given to all participants. General healthy eating advice will also be delivered, roughly in line with UK and US dietary guidelines.

5th contact: Dietary assessments for compliance

1. Video/telephone call. 24-hour food recall, multipass method. ~30-60 mins. (Wks 2, 4, 8)

Participants will have 2 phone calls in weeks 4 and 8, to carry out a 24-hour food recall, a well-regarded measure of dietary intake (45). This will be conducted by an associate nutritionist, with experience of conducting these methods.

Participants will be contacted by the study lead or supervised delegate, to arrange a suitable time for these calls.

As the study is long-term (12 weeks) and free-living, we have built in these compliance checks to allow us to make suggestions to tailor the programme to the needs of the participants if necessary.

7th contact: Clinic visit 2 (Wk 11-12), MRU, KCL. 110 minutes

Participants will attend the MRU, 4th floor, Franklin Wilkins Building, Kings College London for their final engagement. And have the following procedures:

1. Urine samples collected (~0 mins)
2. Blood pressure (~10 mins)
3. Body composition and waist circumference (~10 mins)
4. Fasted bloods (~20 mins)
5. Ultrasound imaging (~30 mins)
6. Heart rate variability monitor fitted (ECG), to keep on for 48-hours (~10 mins)
7. STROOP test (~20 mins)
8. *Optional break for a snack ultrasound.*

Additional measurements made outside of the study visits:

- **4-day diet diaries:** participants will be asked to complete 4-day diet diaries during week 1, week 6 and week 12 of the diet intervention. The 4-day diet diaries are to be completed on non-consecutive days to reflect the intakes of 3 weekdays and 1 weekend day. It will also ask participants to record their satiety from their dinner, on day 1, using 100mm visual analogues scales, at 1-, 2- and 3-hours post meal.
- **Blood pressure** will be taken at home using an automated BP bracelet. Participants will need to put the bracelet on during the study run, and wear it throughout the study. As the bracelet is no waterproof, it will need to be taken off and reapplied after bathing/water activities. It will also need to charged every 25 days and initialized with an accompanying blood pressure cuff to calibrate it.
- **Weight** will be taken by the participant at home, using home weighing scales. Advice will be given on how to standardize these measurements to account for inter and intra variability. This measurement will be taken in the morning before food or drink on even hard flooring at monthly intervals (Table 2). Weighing scales will be provided to participants if they are not in possession of any.

